6.2.4 PREPARATION

There is no medication preparation required.

6.3 MEASURES TO MINIMIZE BIAS: RANDOMIZATION AND BLINDING

There is no randomization in this study. Subjects will be pre-screened prior to clinical visits and all eligible subjects will be approached. Once the controlled strata have been filled then we will no longer approach patients that do not meet criteria for poor asthma control (ACT \geq 19).

6.4 STUDY INTERVENTION COMPLIANCE

We will determine medication compliance by assessing the data collected from the inhaler. These inhalational parameters and medication use data will be transferred from the Digihaler™ to the patients' phone app and then to the server powering the dashboard. If a patient switches to ProAir® Digihaler™ /Airduo™ and determines that one of the inhalers is ineffective they can switch back to their original inhaler and remain in the study. The patient will need to agree to use at least one of the two digital inhalers to remain in the study (ie either the rescue or maintenance inhaler) as this will allow us to obtain the inspiratory parameters required in this study. We also ask that all non-digital inhaler use be documented in the patient diary. We will allow a maximum of 10% of the study population to switch their medications during the study.

6.5 CONCOMITANT THERAPY

6.5.1 RESCUE MEDICINE

The patients will utilize the ProAir® Digihaler™ for rescue. Nebulized albuterol and atrovent will be allowed for severe symptoms during exacerbations and patients will be required to report when these medications were utilized. We will encourage preferential use of the inhaler if symptoms are not severe enough to warrant nebulized medications.

Any concomitant medication a patient is taking at screening and up to the final visit will be recorded on the CRF. Trade name and international nonproprietary name (if available), indication, dose, and start and end dates of the administered medication will be recorded.

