3 OBJECTIVES AND ENDPOINTS

OBJECTIVES	ENDPOINTS	JUSTIFICATION FOR ENDPOINTS
Primary		

To determine the baseline inhalation parameters and patterns of use of both the maintenance (AirDuo®) and rescue (ProAir®) Digihaler™ in patients with severe persistent asthma who are being treated with biologics from baseline through the duration of the 12-month treatment period
	
 • Mean number of daily doses of ProAir® Digihaler™ • Mean number of daily doses of AirDuo® Digihaler™ • Median number of daily doses of ProAir® Digihaler™ • Median number of daily doses of AirDuo® Digihaler™ 	
The number of inhalations of rescue and maintenance bronchodilator use varies amongst and within patients with severe asthma and is impacted by changes in asthma control. This is a clinically meaningful measurement that is included in assessments of disease activity and control. PIF, inspiratory time and volume vary with changes in baseline asthma control and may be important in identifying acute exacerbations of asthma.
 
Maintenance therapies can impact asthma control and confound the response to biologics. In addition, the patterns of use of maintenance therapies and the potential discordance with rescue inhaler use would be important to delineate in this severe asthma population.

Secondary		

To determine the impact of variable degrees of adherence to maintenance therapy on outcomes to biologics. The Digihaler™ will allow us to collect accurate information on adherence that will be utilized to divide patients into groups and to assess asthma outcomes such as change in mean FEV1, exacerbations, oral steroid reduction, and asthma control (using the asthma control
	
 • Proportion of patients with different adherence rates. 
Tests: Summary, chi-squared test, and Tukey’s HSD test statistics of asthma outcomes by adherence group.
	
Adequate understanding of adherence is essential for guiding treatment decisions in clinical asthma care. It may impact response to biologics particularly in patients that are partial responders to targeted therapies. The degree of asthma control while on biologics may be altered by

OBJECTIVES	ENDPOINTS	JUSTIFICATION FOR ENDPOINTS

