5 STUDY POPULATION

5.1 INCLUSION CRITERIA

1. A history of severe persistent asthma as defined by ERS/ATS criteria which includes the presence of poor asthma control on high dose ICS/LABA OR the need for high dose ICS/LABA to maintain asthma control OR oral steroids for maintenance therapy for more than 50% of the prior year.
2. Age >18 years of age or older.
3. Presence of current biologic use or planned initiation of biologics following study enrollment.
4. Patients will be categorized on the basis of asthma control (ACT < 19 will be considered poor asthma control). We will cap the patients with good asthma control at 30% and will no longer enroll those patients once the strata have been fully enrolled.
5. Willingness to switch maintenance inhalers to AirDuo® Digihaler™ and/or to use ProAir® Digihaler™ for rescue therapy. Use of nebulized albuterol will be discouraged but not prohibited. We will require patients to document nebulizer use. Patients that discontinue Pro-Air will be asked to document use of their rescue inhalers in their diaries.
6. Can read and communicate in English and is familiar with and is willing to use his/her own smart device and download and use the study application. If their smart device is not compatible with the study software; willingness to use an alternative device that will be provided by the study team.
7. Ability to provide informed consent.
8. The patient must be willing and able to comply with study requirements and restrictions and to remain at the investigational center for the required duration during the study period, and willing to return to the investigational center for the follow-up procedures and assessments as specified in this protocol.

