8.1.2.4 DIGIHALER™, TEACHING, AND ONLINE APPLICATION

Education for the appropriate use of the Digihaler™ will be provided at the Screening/Baseline visits and again as needed throughout the study. The study team will assist in registering for the digital inhaler application and periodically check to ensure data is being captured appropriately.

Inhalation parameters and number of doses will automatically be collected using the Digihaler™.

Application

The software App is a user facing software/focused smart device application for patients using the Digihaler™ product. The smart device app is used to track medication usage and allow users to self-assess their respiratory symptoms on a daily basis, share information on local environmental conditions, and produce user reports to review data over time.

The software consists of a smart device application compatible for iPhone operating systems (iOS) and Android operating systems that will store data locally on the patient's smart device. The App will receive a patient's health data automatically from the inhaler devices via Bluetooth on a smart device. The smart device camera will be used for scanning and pairing. The data will allow the patient to track their usage of medication, inhalation results, and self-assessments related to their asthma. The App will get environmental information from 1 or more web services.

TEVA Digital Health Platform

The TEVA DHP is a system that stores and transfers health data collected from the App. The cloud solution automatically synchronized with the App after events and/or at predetermined time periods/intervals. An internet connection to the smart device (e.g., wireless or cellular phone network) is required in order for communication to be established between the App and the cloud solution. The

cloud solution will not send any notifications to the App. The cloud solution does not create, modify, or delete patient information.

Patient privacy will be maintained according to the laws and regulations, and patient identifiers will be substituted to maintain a patient's privacy to reviewers of the data.

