9 STATISTICAL CONSIDERATIONS

9.1 STATISTICAL HYPOTHESES

- Primary Efficacy Endpoint(s): Establish group-level daily/weekly baseline normative values for: (1) mean and median number of doses of ProAir® Digihaler™ and AirDuo® Digihaler™, and per-inhalation baseline normative values for (2) peak inspiratory flow (PIF), (3) inspiratory time and (4) volume. We will test the hypothesis that patient-specific baseline usage values are significantly different from usage values collected during or leading up to exacerbation events.
- Secondary Efficacy Endpoint(s): 1. Test the hypothesis that imminent exacerbation events can be predicted using Digihaler™ inhalation parameter measurements. 2. Test the hypothesis that PIF is linearly (or non-linearly) related to FVC and FEV1. Test the hypothesis that there exists a threshold for change in PIF that is associated with a clinically meaningful change (>10%) in lung function. 3. Test the hypothesis that patients with low, moderate, and high adherence to maintenance inhalers have significantly different asthma outcomes. 4. Test the hypothesis that non-responders, partial, and complete responders have significantly different Digihaler™ inhalation parameters. 5. Test the hypothesis that future response to biologics can be predicted using clinical, biological, and digital (inhalation) markers.

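### Rescue use is counted from the ProAir Digihaler alone, so if nebulised rescue takes a larger share around exacerbations, the baseline-versus-exacerbation usage contrast is diluted and could reverse.

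*Combined protocol and SAP*

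**What the plan says.** **How rescue use is measured.** Section 3 lists "Mean number of daily doses of ProAir® Digihaler™" among the primary endpoints, with the median alongside. Section 8.1.2.4 gives the source: "Inhalation parameters and number of doses will automatically be collected using the Digihaler™".

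**What is tested.** Under the primary endpoint, section 9.1 sets the hypothesis that "patient-specific baseline usage values are significantly different from usage values collected during or leading up to exacerbation events".

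**What rescue is allowed off the device.** Section 6.5.1: "Nebulized albuterol and atrovent will be allowed for severe symptoms during exacerbations"; patients must report when they used them. Section 5.1, item 5: "Use of nebulized albuterol will be discouraged but not prohibited. We will require patients to document nebulizer use". Section 6.4 lets a patient return to the original inhaler if at least one digital inhaler is kept, caps switching at 10% of the study population, and adds: "We also ask that all non-digital inhaler use be documented in the patient diary". Section 6.5.1 also has concomitant medication entered on the CRF with dose and dates.

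**What the analysis uses.** Section 9.4.1 joins Digihaler data to medical-record data and questionnaire answers; it does not mention the diary or nebuliser reports. Section 9.4.2 summarises doses by inhaler type and drops data within 14 days either side of an exacerbation from the normative baseline. Section 9.4.3, item 1, builds the exacerbation model from Digihaler inhalation measurements. No section adds off-device rescue to the count, flags the days on which it occurred, or plans a sensitivity analysis for it.

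**The concern.** The route by which rescue drug is taken is not independent of asthma severity. Section 6.5.1 steers patients to the inhaler for milder symptoms and allows the nebuliser for severe ones. The uncounted share of rescue is therefore likely to be larger near an exacerbation than at a patient's baseline, and the loss falls mainly on one side of the section 9.1 contrast.

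The 14-day exclusion in section 9.4.2 protects the normative baseline but not this contrast, because the excluded days are its other side. Section 3 justifies the dose endpoint as a measure of disease activity and control. A reader will therefore take a flat device count around an exacerbation to mean that rescue need did not rise, when part of that need may have been met by nebuliser.

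A separate question is what a day without ProAir data means for a patient who is no longer using, or never used, the ProAir Digihaler. The plan has no rule to distinguish such a day from a day of no rescue use.

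**Working it through.** **The plan's own figure.** The only precision calculation tied to the primary objective (sections 4.2 and 9.2) concerns peak inspiratory flow: SD 15, N=100, half-width 3. It reproduces: 1.96 × 15/√100 = 2.94. It says nothing about rescue use, so the documents contain no figure for this contrast to check.

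**Which window is affected.**
- During the event: directly, through section 6.5.1.
- Leading up to the event: indirectly. Section 5.1 discourages nebulised albuterol but sets no limit on its timing. Section 8.1.2.3 dates onset to the emergency, urgent care or hospital day or, without such contact, to the first dose of oral steroid. Worsening before that date, and any nebuliser use with it, counts as lead-up.

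**Size of the distortion.** Let R be the true ratio of rescue use in the window to baseline, and s and s0 the off-device shares in the window and at baseline.

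Observed ratio = R(1−s)/(1−s0)

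The documents give no value for R, s or s0; all values below are assumptions. With s0=0:

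| R | s=10% | s=20% | s=30% | s=50% | ratio reaches 1.0 at s = 1−1/R |
|---|---|---|---|---|---|
| 1.5 | 1.35 | 1.20 | 1.05 | 0.75 | 33% |
| 2 | 1.8 | 1.6 | 1.4 | 1.0 | 50% |
| 3 | 2.7 | 2.4 | 2.1 | 1.5 | 67% |

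For example, R=2 and s=20% gives 2 × 0.80 = 1.6.

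Baseline off-device use offsets part of this. With s0=5% and R=2, the ratio is 2 × 0.80/0.95 = 1.68 at s=20% and 2 × 0.50/0.95 = 1.05 at s=50%. If s = s0 the ratio is unbiased. Bias toward no difference needs s > s0.

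**What that does to a test.** Section 9.4.2 names no test for this contrast and no length for the lead-up window. As an illustration only, assume a paired two-sided comparison at 0.05 with 80% power under full counting, an unchanged SD and s0=0. The share of the true excess that remains is f = (R(1−s)−1)/(R−1), and power is about Φ(2.80f − 1.96), where 2.80 = 1.96 + 0.84.
- R=2: f = 0.8, 0.6, 0.4 at s = 10%, 20%, 30%; power about 61%, 39%, 20%.
- R=1.5: f = 0.7, 0.4, 0.1; power about 50%, 20%, 5%.
- R=1.5 and s=50%: f = −0.5; the chance of a significant difference in the wrong direction is Φ(1.40 − 1.96), about 29%. The section 9.1 hypothesis is non-directional, so that result would count as support.

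**Days off the ProAir Digihaler.** The section 6.4 cap allows up to 10% × 100 = 10 patients to switch, whichever inhaler they drop. The and/or wording in section 5.1, item 5, may add patients who enrol on AirDuo alone. Non-digital rescue after a switch affects baseline and window alike, so it is mainly a missing-data question and not part of the differential bias above.

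**The case against.** The strongest reply is that nothing is miscounted: the endpoint is defined as ProAir Digihaler doses, and the device counts them. Sections 2.1 and 4.2 present passive recording as the remedy for self-report, so a device-plus-diary composite as the main measure would bring back the weakness the study set out to avoid. This stands, and it is why the endpoint should remain as defined. It does not answer the section 9.1 contrast, which will be read as a statement about rescue need.

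A reader might infer four stronger things that the documents do not support.
- *That rescue is shown to be under-counted before exacerbations.* The direct text concerns use during exacerbations; the lead-up window is reached only by the indirect route above. The records are also left out by silence, not by a stated exclusion.
- *That the exacerbation model rests on dose counts alone.* The inhalation parameters include peak inspiratory flow, inspiratory time and volume, and the feature list in section 9.4.3 is open-ended. The stated question is whether Digihaler measurements predict events; for that question, a fall in device use as patients turn to nebulisers is a real feature of the data.
- *That patients off ProAir are counted as zero rescue.* No section says so; the plan is silent on coding.
- *That the normative baseline is badly distorted.* The 14-day exclusion removes the days on which nebuliser use is most expected.

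The off-device records are also weaker than they may appear. The schedule of activities lists no diary, and section 6.5.1 asks patients to report only when nebulisers were used.

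**Conclusion.** The concern holds for the baseline-versus-exacerbation contrast in section 9.1. The device count can miss rescue use mainly on the exacerbation side, and the plan does nothing with the off-device records it asks for. The result is bias toward no difference, with reversal possible once s exceeds 1 − (1−s0)/R.

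The direction rests on s > s0, which section 6.5.1 makes likely but does not prove. The size cannot be derived from the documents: for R=2 and s0=0 it runs from a modest loss (1.8 at s=10%) to no visible rise (1.0 at s=50%). The descriptive baseline summaries are largely protected. This should be settled before the first analysis; it is not a reason to redefine the endpoint.

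**What to change.** Keep Digihaler doses as the main endpoint and add the following to sections 9.4.2 and 9.4.3, item 1.

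1. Link reported nebuliser and non-digital rescue use (diary and CRF concomitant medication) to the Digihaler data, and flag each patient-day with any such use.
2. For the baseline-versus-exacerbation contrast, add two sensitivity analyses: one on total rescue occasions (Digihaler inhalations grouped into occasions, plus documented off-device treatments), and one that excludes or adjusts for flagged days. Grouping is needed because section 6.2.2 describes one or two inhalations per use, so device doses and nebuliser treatments are not in the same unit. State the grouping rule in advance.
3. Report exacerbation-model performance with and without the nebuliser-day flag. The Digihaler-only model remains the answer to the stated question.
4. For rescue counts, treat days when the patient is not using the ProAir Digihaler as missing, not zero. Identify them from the record of the switch or enrolment choice, not from an absence of device data.

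The cost is data linkage and programming on records the protocol already requests. The downside is that these records are self-reported and may hold only dates of use; in that case the day flag is feasible but the total-occasions analysis may be incomplete. No change to the rescue rules is implied.

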7 STUDY INTERVENTION DISCONTINUATION AND PARTICIPANT DISCONTINUATION/WITHDRAWAL

7.1 DISCONTINUATION OF STUDY INTERVENTION

Patients will be discontinued from study intervention if they are no longer willing or able to comply with study procedures or if they withdraw consent. If a patient switches to ProAir® Digihaler™ /Airduo™ and later has a preference for their original controller or short-acting beta agonist, then switches will be allowed as long as the patient remains on at least one of the two digihaler devices. The patient will need to agree to use at least one of the two digital inhalers to remain in the study (ie either the rescue or maintenance inhaler) as this will allow us to obtain the inspiratory parameters required in this study.

7.2 PARTICIPANT DISCONTINUATION/WITHDRAWAL FROM THE STUDY

1. Patient withdraws consent or withdrawal from the study for any reason
2. Patient experiences an adverse event or other medical condition which indicates to the investigator that continued participation is not in the best interest of the patient.
3. Patient develops an illness that would interfere with his/her continued participation.
4. Patient is noncompliant with the study procedures and assessments in the opinion of the investigator.

Patients should be treated with standard of care after withdrawal from or termination of the study as appropriate. We will obtain information on patients in the case of withdrawal from the study or discontinuation from IMP. Results of any evaluations and observations, together with a narrative describing the reason(s) for withdrawal from the study or discontinuation from IMP, must be recorded in the source documents. The case report form (CRF) must document the primary reason for withdrawal from the study or discontinuation from IMP.

7.3 LOST TO FOLLOW-UP

A patient will be considered lost to follow-up if he/she repeatedly fails to return for scheduled visits and is unable to be contacted by the investigational center.

The following actions must be taken if a patient fails to return to the investigational center for a required study visit:

- The investigational center must attempt to contact the patient and reschedule the missed visit as soon as possible, counsel the patient on the importance of maintaining the assigned visit schedule and ascertain whether or not the patient wishes to and/or should continue in the study.
- In cases in which the patient is deemed lost to follow-up, the investigator or designee must make every effort to regain contact with the patient (where possible, 3 telephone calls and, if

necessary, a certified letter to the patient's last known mailing address, or local equivalent methods). These contact attempts should be documented in the patient's medical record.

- Should the patient continue to be unreachable, he/she will be considered to have withdrawn from the study with a primary reason of 'lost to follow-up'.

8 STUDY ASSESSMENTS AND PROCEDURES

8.1 EFFICACY ASSESSMENTS

The efficacy of the drug product will not be evaluated in this study. The focus of this study is the current behavior of severe asthmatics with regard to their inhaler use.

8.1.1 STUDY VISITS

8.1.1.1 SCREENING/BASELINE VISIT (V0)

Patients will be pre-screened and recruited as they attend standard of care visits in the Severe Asthma Clinic at Michigan Medicine. The following events will take place during the screening/baseline visit:

- Informed Consent
- Enrollment into the MiAsthma Registry
- Review of Inclusion/Exclusion Criteria
- Collection of Medical and Procedure History
- Collection of Smoking/Tobacco Use History
- Review of Past and Current Medications
- Review of Asthma Exacerbations and Healthcare Utilization
- Collection of Clinical Variables (*if available*) including FeNO, CBC w. Differential, and Immunoglobulin E (IgE) Levels
- Dispensation of Inhaler
 - Education on Inhaler Use and Registration to Inhaler Application
- Dispensation of Home Spirometer
 - Education on Use of Home Spirometer
- Collection of Patient Reported Outcomes
 - Asthma Control Test (ACT), AIR-Q, SGRQ

8.1.1.2 IN PERSON/CLINICAL VISITS (V3, V6, V9, V12)

Patients will return to clinic every three months to check in with the study team and to provide additional inhalers for the study. During the in-person visits the following events will take place:

- Review of Current Medications
- Review of Asthma Exacerbations and Healthcare Utilization
- Collection of Clinical Variables (*if available*) including FeNO, CBC w. Differential, and Immunoglobulin E (IgE) Levels
- Dispensation of Inhaler
- Adverse Event Assessment
- Collection of Patient Reported Outcomes

- Asthma Control Test (ACT), AIR-Q, SGRQ
- Device Re-Education (As Needed)

8.1.1.3 INTERIM PHONE CONTACT (V1, V2, V4, V5, V7, V8, V10, V11)

Patients will be contacted monthly between in person visits to assess the following:

- Review of Current Medications
- Review of Asthma Exacerbations and Healthcare Utilization
- Shipping of Inhaler (As Needed)
- Adverse Event Assessment
- Device Re-Education (As Needed)

8.1.2 STUDY PROCEDURES

8.1.2.1 ENROLLMENT INTO MIASTHMA REGISTRY SCREENING/BASELINE VISIT (V0)

All clinical data elements will be abstracted from the EMR and entered into an existing asthma registry at the University of Michigan (MiAsthma Registry) that focuses on severe asthma. A separate consent is required for entry into the database and will be obtained at the same time as initial consent for this study. Variables captured in the MiAsthma Registry include medical and procedure history, review of past and current medications (both asthma and non-asthma related) and collection of clinically assessed PRO's. Relevant medical history may include any of the following: asthma history, co-morbid conditions such as nasal polyps, allergic rhinitis, hives, eosinophilic disease other than asthma, obesity and sleep apnea, age of asthma onset, number of exacerbations in the past year, lifetime hospitalizations, yearly ER visits, oral steroid dependence, history of life-threatening asthma as indicated by prior intubation and mechanical ventilation.

